person-time where person-time is defined as the amount of time a patient is followed from study start to either the end of study, death or loss to follow-up (whichever occurs first). We will also compute summary statistics (mean, median, standard deviation, range) for length of hospital stay, health-related quality of life, quality of surgical care and recovery to independent living. We will make assessments overall and by treatment group. While our emphasis is to assess feasibility, we will also attempt to assess if differences exist between the intervention and control conditions with regards to these post-operative measures.

D.11. Justification of Pilot sample size. Based on the historical surgical volume at VAPHS, the participating surgical services will treat 54 eligible patients who meet our inclusion criteria during a 7 month recruitment window (Table 3). We are not estimating the effect size between intervention and control conditions. Although there is a tradition of using pilot studies to do so, there is growing consensus that this approach is ill-founded because the small samples result in imprecision that makes power estimates unreliable.²³ Therefore, based on recruitment and retention rates estimated here (Aim 1), we will power our subsequent study based on “minimum clinically meaningful differences” defined for each outcome *a priori*.²⁴

Table 3: Sample Size Estimates	General	Urology	Total
Total Surgical Cases/year	1488	610	2098
VASQIP Eligible Cases/year	748	298	1046
Proportion Abdominal	56.2%	35.3%	$\bar{x}=50.2\%$
Proportion Frail	12.0%	10.3%	$\bar{x}=11.5\%$
Eligible Cases/year	70.9	21.5	92.4
Eligible Cases/7 month recruitment	41.4	12.5	53.9

References:

* Please provide a list of references (Multi-site protocols: You may reference the page numbers in the original protocol):

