- (3) Estimate overall and treatment-specific summary statistics for postoperative outcomes in terms of 30- and 90-day (a) mortality, (b) major complications, (c) length of hospital stay, (d) health-related quality of life, (e) quality of surgical care, and (f) change in level of independent living.

Methods: This randomized pilot study will enroll a consecutive cohort of up to 50 Veterans identified as frail using a standardized frailty assessment and scheduled for major abdominal surgery on the general or urological surgery services at the VA Pittsburgh Healthcare System. We will randomize participants 1:1 to receive either: (1) standard preoperative optimization by the Interdisciplinary Medical Preoperative Assessment Consultation & Treatment Clinic (IMPACT), or (2) prehabilitation + standard IMPACT optimization. The 6-week long prehabilitation intervention

will include (1) strength and balance training; (2) inspiratory muscle training; and (3) nutritional coaching and supplementation. Assessments will include standard postoperative outcomes as well as the Short Physical Performance Battery to measure physical performance, Maximal Inspiratory Pressure to measure pulmonary function, and both prealbumin and the 7-point Subjective Global Assessment to measure nutrition. Outcomes will be assessed 30 or 90 days after surgery. Compliance with the prehabilitation regimen will be assessed through patient logs and pedometers. Analyses will inform the development of a larger randomized controlled trial testing the prehabilitation intervention. Findings will be relevant for the as many as 42,000 frail Veterans scheduled for major elective surgery each year.

*** Describe the study objectives. Please include primary aim and hypothesis, if applicable any secondary aims and hypotheses.**

We will examine the feasibility of a novel, multifaceted pre-habilitation intervention aimed at improving postoperative outcomes for frail Veterans undergoing major abdominal surgery. Specific aims are to:

- (1) Estimate rates of recruitment, randomization, retention, and compliance with the prehabilitation intervention;
- (2) Measure (a) physical performance, (b) pulmonary function, and (c) nutrition at baseline and 2-week intervals to estimate changes over time and explore the optimal duration of prehabilitation (2 vs. 4 vs. 6 weeks); and

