*** Research Procedures/Interventions:**

D.1. Overview. We will conduct a randomized pilot study of a prehabilitation intervention in a consecutive sample of up to 50 frail patients scheduled for elective major abdominal surgery at the VAPHS. Participants will be recruited from the mandatory preoperative IMPACT clinic where all patients are routinely screened for frailty. Frail patients agreeing to participate will be randomized 1:1 to (a) standard preoperative optimization by the IMPACT clinic or (b) prehabilitation + standard IMPACT optimization. The prehabilitation intervention will deploy existing cardiac rehabilitation resources to provide (a) strength and balance training, (b) respiratory muscle training, and (c) nutritional coaching and supplementation. Using physical performance tests, biomarkers, chart review, survey instruments, and patient logs, we will assess the feasibility of the recruitment, randomization, retention and assessment procedures, compensating patients for their time.

D.4. Eligibility criteria. We will include all patients with RAI>16 scheduled for major abdominal surgery on the general or urological surgery services. Major surgery is defined according to VASQIP criteria to include cases requiring general, epidural, or spinal anesthesia.

For general and urological surgery, it includes 270 standard, 356 intermediate, and 34 complex procedures, but excludes 291 low risk, "minor" surgical procedures with limited morbidity (e.g., abscess drainage, lipomas, or hemorrhoids). From these major surgeries, we will include those abdominal procedures that deliberately violate the peritoneal or retroperitoneal spaces. For example, from the general surgery service we will include all bowel resections, biliary procedures, and abdominal wall reconstructions, but exclude open, anterior inguinal hernia repair. The list of included CPT codes (see Appendix) represents 56% and 35% of the general and urological surgery volume at VAPHS, respectively (Table 2 below). Given the burden of comorbidity among the frail, we anticipate that many eligible Veterans will have concurrent cognitive impairment or dependent living situations. These limitations need not preclude inclusion so long as the patient can provide first-person informed consent and participate in the prehabilitation regimen described below (D.6). No other exclusions are planned.

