D.5. Randomization procedures and their rationale. Some patients may be reluctant to accept the possibility of randomization to control conditions, and if so, recruitment rates of a randomized trial would be diminished. We will therefore use the randomization feature in REDCap to randomize participants in a 1:1 ratio. As each patient enrolls, REDCap will assign the patient to intervention or control conditions as specified by a fixed allocation table. If patients refuse participation based on the risk of randomization, we will note this fact, but offer the opportunity to participate in the preferred arm (intervention or control). This approach will permit accurate estimates of randomization while accruing the largest possible sample size.

D.6. Prehabilitation Procedures.

(a) Overview. Prehabilitation will include hospital- and home-based components within an integrated intervention led by [name]. The hospital-based component will occur at the VAPHS Cardiac Rehabilitation facility and focus on supervised strength and balance training. One-hour sessions will be scheduled twice weekly for at least 4, but no more than 6 weeks before the operation. The home-based component will entail walking or seated pedaling on a home exerciser, as well as Respiratory Muscle Training (RMT), both of which are feasible and safe to do in a non-supervised setting. Nutritional supplementation will be linked to the composite training protocol. Compliance will be measured with exercise log books (See Appendix) and pedometers given to each participant. With the consent of the surgeon, operative dates will be scheduled to accommodate prehabilitation.

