(b) Missing Data Strategies. We will attempt to minimize the amount of missing due to dropouts (withdrawals, lost to follow-up, or deaths) or individuals who missed at least one of the follow-up assessments (intermittent missing). In the event of missing data, we will use multiple imputation to impute the missing values.

(c) Estimate rates of recruitment, randomization, retention, and compliance with the prehabilitation intervention [Aim 1]. To assess the feasibility of recruitment, randomization, and retention, we will summarize the total number of eligible patients approached, recruited, randomized to intervention and control conditions, and retained through the completion of study procedures 90 days postoperatively, estimating rates as well as associated confidence intervals.²⁵ For those lost to follow up, we will estimate the proportion of planned in-hospital prehabilitation sessions completed before dropping out along with rates of 30-day outcome assessment (if available). For those randomized to the intervention condition, compliance with the hospital-based regimen will be measured as the number of scheduled sessions completed. If patients are able to comply with only a portion of the training regimen, this will be noted and the patient will be categorized as partially compliant. Compliance with the home-based regimen will be measured as the number of assigned activities documented in the patient logs. Overall compliance rates with confidence intervals (CIs) will be estimated for the home, hospital, and combined intervention. We will also compute rates (and CIs) of partial compliance as well as rates (and CIs) of intervention-specific task compliance.

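### The planned comparison of post-operative outcomes between arms is not restricted to randomized participants, although patients who refuse randomization may choose their arm, and it sits uneasily with D.11

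*Combined protocol and SAP*

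**What the plan says.** The study is a pilot in "a consecutive sample of up to 50 frail patients scheduled for elective major abdominal surgery at the VAPHS" (D.1), and the Abstract says "We will randomize participants 1:1 to receive either" standard optimization or prehabilitation plus standard optimization.

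D.5 adds a second way in. If a patient declines because of randomization, staff record this but "offer the opportunity to participate in the preferred arm (intervention or control"). The stated aim is to measure willingness to be randomized while enrolling as many patients as possible.

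D.10(e) gives event rates for all patients and by treatment group, with CIs, and summary statistics for the remaining outcomes, again overall and by group. After noting that feasibility comes first, it then says: "we will also attempt to assess if differences exist between the intervention and control conditions with regards to these post-operative measures". It names no analysis population, test, significance level, number of comparisons or multiplicity rule, and does not label the comparison exploratory.

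D.11 follows directly: "We are not estimating the effect size between intervention and control conditions". Its reason is that small pilot samples are too imprecise to support power estimates. Instead, "we will power our subsequent study based on" minimum clinically meaningful differences set in advance, together with the Aim 1 recruitment and retention rates.

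**The concern.** The first issue is who is compared. Frail patients who ask for supervised exercise may differ from those who ask for usual preparation in motivation, mobility, transport or support at home. These traits plausibly affect recovery. If such patients are pooled with randomized patients, the arm difference mixes treatment with self-selection.

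The second issue is what the comparison can show. D.11 regards between-arm estimates from a sample this small as too imprecise to plan on. A judgment on whether the arms differ rests on the same data and inherits the same imprecision. With no test or list of comparisons fixed in advance, an analyst could examine any of six outcome domains and report any of them.

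The Abstract says the analyses will inform a larger randomized trial. A biased difference, an uninformative null or an isolated significant result could each color that work.

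**Working it through.** **1. Who enters the comparison.**

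- D.5 uses the same two labels, intervention and control, for the arms assigned by REDCap and for the arms that refusers may choose.
- D.10(c) limits its compliance measure for the hospital sessions to patients randomized to the intervention. D.10(e) carries no such limit and refers to all patients and to treatment groups.

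On the text as it stands, a patient who chose an arm is counted in that arm for Aim 3.

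**2. Form of the bias.** Let f_I and f_C be the shares of each arm that chose it. Let d_I and d_C be the differences in expected outcome between self-selected and randomized patients in the same arm. Then:

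expected difference, everyone = expected difference, randomized + (f_I × d_I − f_C × d_C)

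The extra term does not contain the sample size, so enrolling more patients does not shrink it. The documents give no value for any of the four quantities, so no numerical size can be stated.

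**3. Sample size.** The plan states no power. Its only derived figure is in Table 3: 92.4 eligible per year × 7/12 = 53.9, which reproduces. The enrollment cap of 50 at 1:1 gives at most 25 per arm. Fewer is possible:

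- Refusers reduce the randomized number.
- No dropout rate is given; the share "retained through the completion of study procedures 90 days postoperatively" is itself an Aim 1 estimate.
- The rows of Table 3 multiply to 748 × 0.562 × 0.120 = 50.4 plus 298 × 0.353 × 0.103 = 10.8. That is 61.3 per year before rounding, or 35.7 in 7 months: about 18 per arm if all enroll. This mismatch with 92.4 is a separate matter, used here only to set a lower case.

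**4. Power.** Assumed: two-sided 5% tests. For proportions p1 and p2 with mean p̄:

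power = Φ{ [|p1 − p2| − 1.96 √(2p̄(1 − p̄)/n)] / √[p1(1 − p1)/n + p2(1 − p2)/n] }

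For means: power = Φ{ δ / (SD √(2/n)) − 1.96 }

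Effect sizes from the documents: relative risk 0.67 for complications with nutritional support (D.6(d)); relative risk 0.48 for pulmonary complications with inspiratory training (D.6(c)); minimum important difference 0.06 on the AQoL-6D (D.8). They are cited there as background and are not design assumptions. Control rates and SDs are assumed.

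| Effect | Assumed input | 25 per arm | 18 per arm |
|---|---|---|---|
| RR 0.67 | control 10% | 6.2% | 5.4% |
| RR 0.67 | control 20% | 9.0% | 7.6% |
| RR 0.67 | control 30% | 12.3% | 10.0% |
| RR 0.67 | control 40% | 16.4% | 12.9% |
| RR 0.48 | control 20% | 17.5% | 13.7% |
| RR 0.48 | control 30% | 26.0% | 19.8% |
| AQoL 0.06 | SD 0.15 | 29.3% | 22.4% |
| AQoL 0.06 | SD 0.30 | 10.5% | 8.7% |

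Worked example, RR 0.67 at a 20% control rate and 25 per arm: p1 = 0.20, p2 = 0.134, p̄ = 0.167. Power = Φ[(0.066 − 1.96 × 0.1055)/0.1051] = Φ(−1.34) = 9.0%. The 95% CI half-width is 1.96 × 0.1051 = 0.206, or about 21 points around a 6.6-point difference.

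Pushing RR 0.48 to a 40% control rate raises power to 36%. Fisher's exact test lowers it: RR 0.67 at 20% falls from 9.0% to 4.6%. For 80% power at 25 per arm, the standardized difference must be (1.96 + 0.84) × √(2/25) = 0.79.

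**5. Multiplicity.** Six domains tested once each give 6 tests. Table 1 supports about 8 post-operative comparisons: mortality (2), living location (2), complications (1), length of stay (1), quality of life (1) and post-operative quality of surgical care (1). Taking complications at 90 days too, as D.10(e) says, makes 9. With independent tests at 5%:

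- 6 tests: 1 − 0.95^6 = 26.5%
- 8 tests: 1 − 0.95^8 = 33.7%
- 9 tests: 1 − 0.95^9 = 37.0%

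Fisher's test is conservative at this size: its actual level at 25 per arm is 0.03% for 4% mortality and 2.2% for 20% complications. With Fisher used for those two outcomes, the 8-test figure is 1 − 0.95^5 × 0.9997² × 0.978 = about 24%. Correlation between outcomes would usually lower it further.

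**The case against.** The strongest reply is that D.11 has a narrow purpose: it explains why a pilot effect estimate should not drive the power of the next trial. D.10(e) ranks the comparison behind feasibility and promises only an attempt. A secondary look that never feeds a power calculation is compatible with both. This stands. A reader might infer that the two statements cannot both be followed, but the documents do not support that; they pull against each other. A reader might also infer that D.11 has already given up p-values, but it mentions neither p-values nor tests.

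It is also fair that D.10(e) names no test or significance level. Every power and error figure above therefore depends on assumed 5% tests, and the control rates and SDs are assumed too.

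Finally, no go/no-go rule is tied to Aim 3, so harm to the later trial is possible but not built into the plan.

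None of this answers the population gap. That gap depends on no assumed rate and remains whether the comparison is made by test, by CI or by eye.

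**Conclusion.** The point holds. As written, D.5 and D.10(e) together allow self-selected patients into the arm comparison, which can bias it by an amount the documents do not allow one to calculate. This is the main defect.

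The tension with D.11 is real but secondary. With two-sided 5% tests and the assumed control rates and SDs, power at 25 per arm is roughly 6% to 29%. Even the extreme case in the working reaches only 36%. Family-wise error is about 26% to 37% for 6 to 9 independent tests, and less with correlated outcomes or Fisher's test.

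Two stronger readings should be avoided:

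- **Twelve tests.** The Aim 3 wording puts both time points before all six domains, so a reader might count 12 tests and quote 1 − 0.95^12 = 46%. Table 1 does not schedule 12: length of stay has one value per patient, and post-operative quality of life and surgical-care quality are each measured once.
- **An isolated significant result is probably false.** Family-wise error is not that probability. If effect and no effect are taken as equally likely beforehand (an assumption), the share of significant results that are true is power/(power + 0.05): 0.06/0.11 = 55% at the low end and 0.29/0.34 = 85% at the high end. The documents give no prior that would support the stronger claim.

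**What to change.** In D.10(e), replace the sentence on assessing differences with text to this effect: between-arm differences in post-operative outcomes are exploratory; they will be presented as estimates with 95% CIs, in randomized participants only and according to the arm assigned; participants who chose their arm will be summarized separately; no conclusion about efficacy will be drawn.

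Reword D.11 as well. If D.10(e) reports differences with CIs, the flat statement that no between-arm effect is estimated would no longer be true. D.11 should say instead that any between-arm estimates from this pilot will not be used to size the later trial.

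The cost is a few sentences, a somewhat smaller sample for the arm comparison and no p-values. Participants who chose their arm can still be enrolled as D.5 intends, and the refusal count still serves the Aim 1 estimate of willingness to be randomized.

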A.3. Frail Veterans frequently undergo major surgery with dramatically increased morbidity and mortality. Some form of frailty is present in half of all Veterans undergoing colorectal and cardiac surgery,⁵ and one third of the US population is expected to undergo a major surgical procedure within the last year of life.⁴⁵ Some frail patients clearly benefit from surgery through improved symptom management and extended life. However, the high rate of surgical morbidity and mortality among the frail suggests that for many, surgery confers significant burdens for patients, families, and society at large.⁴⁻⁹ For example, compared to robust patients, frail surgical patients are less likely to be discharged to home,⁸ more likely to be readmitted within 30 days,^{5,9} and have substantially increased rates of perioperative mortality and complications.^{4,6,7,9} In fact, our preliminary analysis demonstrates similar patterns across 1,632 major abdominal operations performed at VAPHS from 2010 to 2014 where 192 (11.8%) Veterans with differing degrees of frailty suffered dramatically increased mortality, morbidity and length of stay. Even in the mildly frail, 30-day postoperative mortality was 10 times greater than among the robust (4% vs. 0.4%, $p < .001$), and increased dramatically with increasing frailty. However, little is known about how to improve the surgical outcomes of frail patients.

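### Table 3's input rows multiply to about 36 eligible patients in 7 months, not the 54 stated in D.11

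*Combined protocol and SAP*

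**What the plan says.** D.11 (Justification of Pilot sample size) rests on one number: "the participating surgical services will treat 54 eligible patients who meet our inclusion criteria during a 7 month recruitment window (Table 3". Table 3 is the stated source. For general surgery and urology it lists total cases per year ("Total Surgical Cases/year 1488 610 2098"), VASQIP-eligible cases (748 and 298), the abdominal proportion (56.2% and 35.3%) and the frail proportion (12.0% and 10.3%). It then gives eligible cases per year as 70.9 + 21.5 = 92.4. The last row, "Eligible Cases/7 month recruitment", gives 41.4 + 12.5 = 53.9. No formula is printed, and no further filter or multiplier is described.

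D.4 (Eligibility criteria) defines major surgery by VASQIP criteria and continues: "From these major surgeries, we will include those abdominal procedures that deliberately violate the peritoneal or retroperitoneal spaces". It says that the included procedure codes "represents 56% and 35% of the general and urological surgery volume at VAPHS, respectively". D.1 sets enrolment at "a consecutive sample of up to 50 frail patients scheduled for elective major abdominal surgery at the VAPHS". Section A.3 of the background gives a separate local series: "across 1,632 major abdominal operations performed at VAPHS from 2010 to 2014 where 192 (11.8%) Veterans with differing degrees of frailty".

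**The concern.** Read from top to bottom, Table 3 narrows the yearly caseload to VASQIP-eligible, then abdominal, then frail cases, and the next row should be the product. It is not. The printed yearly count is about one and a half times the product, and D.11 carries the excess into the text.

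The figure matters because D.11 offers no other quantitative support for the pilot size or the 7-month window. A pool of 54 lies just above the ceiling of 50, so the plan looks attainable if nearly everyone consents. A pool of about 36 cannot yield 50 in 7 months at any consent rate. D.11 also says that the later trial will draw on the recruitment and retention rates estimated here, and those rates would be less precise with a smaller pool.

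**Working it through.** **Inputs.** All are from Table 3 unless stated: VASQIP-eligible cases 748 and 298; abdominal 56.2% and 35.3%; frail 12.0% and 10.3%.

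**What reproduces.** The column sums hold (70.9 + 21.5 = 92.4; 41.4 + 12.5 = 53.9), and 92.4 × 7/12 = 53.9. The last row therefore follows from the row above it, and the break enters at the yearly eligible count.

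**What does not.** Yearly eligible cases = VASQIP-eligible × abdominal × frail:

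| | Product per year | Printed | Printed ÷ product |
|---|---|---|---|
| General | 748 × 0.562 × 0.120 = 50.45 | 70.9 | 1.41 |
| Urology | 298 × 0.353 × 0.103 = 10.83 | 21.5 | 1.98 |
| Total | 61.28 | 92.4 | 1.51 |

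Over 7 months: 61.28 × 7/12 = 35.7 (general 29.4, urology 6.3), against 53.9. The two services are off by different factors, so no single missing multiplier explains the gap.

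**Rounding.** Moving all four percentages to their rounding limits gives 35.6 to 35.9. The gap is 18 patients.

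**Other readings, per 7 months.**
- All surgical cases as the base: (1488 × 0.562 × 0.120 + 610 × 0.353 × 0.103) × 7/12 = (100.35 + 22.18) × 7/12 = 71.5. This also implies 1488 × 0.562 = 836 general abdominal cases, more than the 748 major cases from which D.4 draws them.
- No abdominal step: (748 × 0.120 + 298 × 0.103) × 7/12 = 120.45 × 7/12 = 70.3.

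**What the printed counts would require.**
- Abdominal share, with the frail row kept: 70.9 / (748 × 0.120) = 79.0% and 21.5 / (298 × 0.103) = 70.0%. With rounding these are 78.6–79.4% and 69.5–70.6%, against 56% and 35% in both Table 3 and D.4.
- Frail share, with the abdominal row kept: 70.9 / (748 × 0.562) = 16.9% and 21.5 / (298 × 0.353) = 20.4%. This also reverses the order of the two services.

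**Cross-check with A.3.** Abdominal cases per year in Table 3: 748 × 0.562 + 298 × 0.353 = 525.6. At the 11.8% frailty that A.3 reports among major abdominal operations, 525.6 × 0.118 = 62.0 a year, or 36.2 in 7 months. The printed total needs 92.4 / 525.6 = 17.6%.

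**Consequence if the input rows are right.** The consent rates are assumptions.

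| Consent | Enrolled in 7 months (pool 35.7) | Enrolled in 7 months (pool 53.9) | Months to 50 (pool 35.7) |
|---|---|---|---|
| 100% | 36 | 54 | 9.8 |
| 80% | 29 | 43 | 12.2 |
| 60% | 21 | 32 | 16.3 |

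Suppose all eligible patients are approached and half are recruited (both assumptions). The exact 95% interval for the recruitment rate then has a half-width of 13.9 percentage points with 54 eligible patients and 17.1 with 36.

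**The case against.** The strongest reply is that the product need not equal the eligible count. It does so only if the frail row is measured among abdominal cases, and the table suggests a wider denominator. Its printed mean of 11.5% matches weighting by VASQIP cases (11.52%) or by all cases (11.51%), whereas weighting by abdominal cases gives 11.66%. If eligible cases were counted directly, every number could be right and only labels would be missing. That possibility stands, and the documents do not exclude it. It would, however, need 17.6% frailty among abdominal cases, where A.3 reports 11.8%. A.3 is weak evidence, because it is a different series whose services are not stated.

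Mixed bases are also possible. On the all-cases base, urology alone comes to 22.2 a year, close to the printed 21.5, although its rounding limits (22.0 to 22.3) exclude that value. General surgery fails clearly on that base (100.4 against 70.9). This may hint at how the error arose, but it does not give 54.

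The agreement of D.4 with the abdominal row is not independent confirmation, since both may come from one source.

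Finally, the practical harm is limited. Fifty is a ceiling, no feasibility threshold is tied to it, and no power calculation uses 54. For Aim 1, D.10(c) says "we will summarize the total number of eligible patients approached, recruited, randomized to intervention and control conditions", so the rates rest on patients actually counted and a shortfall would be seen. All of this stands. It limits the severity but leaves the table unexplained.

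**Conclusion.** The concern holds. As printed, Table 3 does not support 54 eligible patients in 7 months; its input rows give about 36 (61.3 a year against 92.4). Confidence is high that the figure cannot be reproduced. It is lower that 36 is the true pool, because that assumes the VASQIP base and the same frailty in abdominal cases as in the frail row. D.4 favours the VASQIP base and A.3 weakly favours the frailty rate, but the documents do not settle which rows are wrong.

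This should be fixed, because D.11 relies on the figure for both the size and the window. It does not invalidate the design or bias the Aim 1 estimates. If the input rows are right, the effect is a smaller expected sample and wider intervals.

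**What to change.** Check the source counts, then state under Table 3 the formula and the denominator of each proportion. What follows depends on the result:

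- If the input rows stand, change the yearly row to 50.4 / 10.8 / 61.3 and the 7-month row to 29.4 / 6.3 / 35.7, and change the 54 in D.11 to about 36. The yearly total is summed before rounding.
- If the eligible counts stand and an input row is wrong, correct the abdominal or frail row and, where affected, the 56% and 35% in D.4.
- If the eligible counts came from a direct count and the rows have different denominators, say so and give the frailty among abdominal cases that the count implies.

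It would also help, though the correction does not depend on it, to give the enrolment expected in 7 months at a stated consent rate.

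The cost is a check of source counts and a correction to the table and text. The corrected figure may be less favourable. No extra patients are required. A longer window would be the sponsor's choice and would cost time and staff.
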